1.3.1 Participants eligibility

The inclusion criteria of participants includes: (a) English-speaking, (b) community dwelling, (c) members of PRP registry, (d) prefrail (evaluated by the Fried's Frailty Criteria Index), (e) self-identify as African Americans, (f) aged 55 and older. The exclusion criteria include: (a) diagnosed psychiatric disorders, (b) moderate or severe cognitive impairment (verified using the validated 6CIT and operationalized as score of ≥ 10),⁶⁸⁻⁶⁹ the use of prescription drugs that could affect cognition and functioning (e.g., neuroleptics), (c) individuals with typical daily pain ratings of $\geq 7/10$, (d) plan to change residences during the study period; (b) rely on a wheelchair for home or community mobility; (e) are actively receiving home care services, occupational, or

physical therapy; (f) are on dialysis or who have an end stage disease (e.g., stage IV heart failure); (g) are enrolled in a health promotion program focused on PA and diet; and (h) those who have a baseline dietary quality score of $\geq 85/100$ as their diet would already be very close to ideal (average score for U.S. population = 59).

Figure 2. Overview of the SHAPE pilot study.

Raters will conduct the activities in the navy boxes.

1.3.2 Phone screening

The study coordinator calls potential participants from the participant resource pool (PRP) registry to screen for exclusion criteria (a)-(g). If potential participants passed the phone screening, the coordinator will schedule consent/baseline evaluation visit and assign 1-2 raters for the visit.

1.3.3 Consent visit

Consenting visits will take place at participants' home. Raters should call potential participants 1 day ahead of time to confirm if they are still available. During the visit, raters will explain and help participants understand the SHAPE study procedure. All components of the consent form should be clearly delivered (see 2.3 consenting procedure). Consent forms must be attained before any data collection activities started. Both potential participants and the raters will sign two copies of consent forms, one for the potential participants to keep and one for the lab.

1.3.4 Baseline evaluation

[figure not shown]
Ideally, once potential participants consented, raters will immediately start the baseline evaluation. However, if the potential participant need time to think about joining the study or are unwilling to do the baseline evaluation immediately after consent, raters should reschedule another time for baseline evaluation visit (figure 2).

At baseline evaluation visit, the raters will collect potential participants' sociodemographic characteristics and anthropometrics. A series of psychometric and performance-based measurers will also be conducted for eligibly confirmation and primary/secondary outcomes (table 2; see 1.4.2 for procedure of measurement administration). Most of the measures will be conducted in the baseline evaluation visit, except for ActivPal activity-tracking device (measures sedentary time) and Automated Self-Administered 24-hour (ASA24) dietary recall (measures dietary quality).

Sedentary time is measured by Community Healthy Activities Model Program for Seniors (CHAMPS) and the ActivPal activity-tracking device. At baseline evaluation visit, the rater will teach potential participants to use the ActivPal activity-tracking device. The potential participant will wear the ActivPal sensor for **seven consecutive days** to collect baseline activity data.

At the end of the tracking period, the rater will schedule an

Figure 3. Breakdown of baseline evaluation by tasks

ActivPal pick-up visit to retrieve the tracker from the participant.

To evaluate potential participants' dietary quality, the rater will administer two ASA24 dietary recalls in two non-consecutive days. The ASA24 is a web-based tool that enables multiple, automatically coded, self-administered 24-hour recalls for multiple meals. At baseline evaluation visit, raters will log in to the ASA24 system respondent website to go collect recalls of meals dietary from the previous day. **A 2nd ASA24 phone follow-up will be scheduled** two days after the baseline evaluation will be conducted to collect another day of participants' dietary intake.

After completing consent/baseline evaluation visit, all files and tools should be returned to the [name] lab in the same day. If raters need to return the tools overnight, please remember not to leave the tools in raters' car, some tools need to be in certain temperature.

1.3.5 Randomization and Blinding

After consent/baseline evaluation visit. The study coordinator will check participants' eligibility. Randomization was carried out by a coordinator not involved in data collection or analysis activities. Data collectors were blinded to arm assignment.

Participants will be allocated using a 1:1 ratio via adapted randomization sequences generated *a priori* by the study statistician, [name], using an online tool (<https://www.sealedenvelope.com/simple-randomiser/v1/lists>) to form a randomization table with a variable block size (2,4, or 8). Randomization sequence concealment will be achieved by query of the REDCap (Research Electronic Data Capture) system.

1.3.6 Recruitment

Participants are recruited through PRP list from the Healthier Black Elders Center (HBEC). A preidentified list was screened by the center coordinator. Raters cold call people on the list to invite potential participants to join our study.

1.3.7 Intervention period

The treatment group will receive habit formation intervention for 12 weeks. The HF intervention is delivered by an experienced geriatric occupational therapist. The 12-week long, intervention is delivered to each participant during 12 face-to-face, home based sessions (each lasting ~60 minutes). An initial session (week 2) focuses on welcoming the participant to the program, and delivering educational content about prefrailty, frailty protective behaviors, and the concept of HF. In preparation for the sessions covering ST reduction and MVPA the next session (week 3) focuses on pain, its management, and the relationship between pain and activity (described below). Weeks 3-11 include weekly HF sessions focused on ST reduction, MVPA and dietary behaviors (see Table 2 for session content). A closing session occurs in week 12 to review program progress and create maintenance plans.

The control group will receive 12 weeks of newsletters focused on general healthy aging topics. Within 4 days of mailing the newsletter, the coordinator will call the participant, verify receipt of the newsletter, and ask them if they have any questions about the materials. Phone

call will last ~15 minutes. Control condition participants receive no further intervention.

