Effective frailty reduction interventions delivered to older African Americans during the prefrailty stage could reduce or delay frailty and improve health outcomes among older African Americans. For prefrail older adults, the progression to frailty is neither inevitable nor irreversible. Pre-frail elders can regain non-frail resilience and are significantly more likely to do so than frail elderly.^{5, 22-24} Moreover, pre-frailty represents an important, time-limited window of opportunity to intervene in the progression to frailty.²⁵ A recent study suggested that individual's spend approximately 7.4 years in the prefrail stage versus only 3.4 in the frail stage (before progressing to death or disability).²⁵ Interventions delivered during prefrailty may also require less intensive treatment than those delivered during frailty. Resilience-bolstering behaviors such as consuming adequate nutrition and increasing physical activity (PA) levels are currently the frontline non-pharmacological treatment for frailty reduction. Adequate nutrient intake (e.g., protein, vitamin D, fatty acids and minerals) protects against frailty by improving cell metabolism and anabolic signaling.²⁶ PA is considered frailty-protective through the effect that it has on attenuating sarcopenia,²⁶⁻²⁷ stimulating muscle protein synthesis,²⁸⁻²⁹ and

increasing muscle strength, and physical performance.²⁶⁻²⁷ Thus, intervening to increase physical activity and improve dietary quality among older adults during the prefrailty stage has the potential to reduce prefrailty and significantly improve both current and future health.

A novel, evidence-based habit formation program is used the SHAPE study to improve dietary quality and decrease total sedentary time (ST) could reverse prefrailty or delay its progression among older adults. The habit formation program consists of 12 treatment sessions over 12 weeks. In each session, an occupational therapist will deliver educational content, and use HF techniques and behavioral skills to facilitate frailty protective behaviors. The conceptual treatment model approach to improve dietary quality and reduced ST among frail older adults (Error! Not a valid bookmark self-reference.). HF approaches are effective across a range of behaviors, easy to implement, satisfactory to participants, tailorable to the individuals' unique context, and correlated with key health outcomes.^{54, 63-65}

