1.3.8 Follow-up data collection

When the 12-week intervention period is over, the coordinator will assign raters for follow-up evaluation. Most of the measures will be re-administered.

Table 1 Overview of measurements and testing time

Evaluation time point (week)	Variable	Measure
Screening		
Phone screening (w0)	Eligibility	1. Phone screening eligibility form
	Frailty status	2. Paulson Lichtenberg Frailty Index (PLFI)
	Cognitive impairment	3. The Six Item Cognitive Impairment Test (6CIT)
Primary outcome*		
Baseline (w1), follow-up (w15)	Sedentary time	4. Community Healthy Activities Model Program for Seniors (CHAMPS)
Baseline evaluation (w1- 2), follow-up (w15)	Sedentary time	5. ActivPal kcal expenditure
Baseline (w1, 2 nd phone follow-up), follow-up (w15, 2 nd phone follow-up)	Dietary quality	6. Automated Self-Administered 24-hour (ASA24) dietary recall
Secondary outcome		
Baseline (w1), follow-up (w15)	Frailty status	7. The Fried's Frailty Criteria 
 • Grip strength with dynamometer • 15 ft walking test
	Lower extremity muscle strength	8. Short Physical Performance Battery (SPPB) 
 • 3-meter walking test
	Balance	
	Quality of life	9. The World Health Organization Quality of Life- BREF (WHOQOL-BREF)
Habit formation (Treatment group only)	Habit formation	10. The self-reported habit index subscale
Demographics and other mediators		
Baseline (w1)	Comorbidities	11. Comorbidity Checklist
	Sociodemographic	12. Sociodemographic Form
Baseline (w1), follow-up (w15)	Participants anthropologies	13. Participants anthropologies forms 
 • Weight • Height • Waist circumference
	Depressive symptoms	14. Geriatric Depression Short form (GDS)
Treatment session 1,3,5,7,9 (w 3, 5, 7, 9, 11)	Habit formation	15. Self-report habit index (SRHI)

Note. *Both primary outcomes will be used for screening potential participants' eligibility.

2. Data analysis plan

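### Do the mismatched week and session labels leave the follow-up time or the baseline period in doubt?

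*Combined protocol and SAP*

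**What the plan says.** Three places in the combined protocol and SAP give the calendar.

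- **Programme.** Section 1.2: "The habit formation program consists of 12 treatment sessions over 12 weeks". Section 1.3.7 gives the same totals and then labels the weeks: "An initial session (week 2) focuses on welcoming the participant to the program"; "the next session (week 3) focuses on pain"; "Weeks 3-11 include weekly HF sessions focused on ST reduction, MVPA and dietary behaviors"; "A closing session occurs in week 12 to review program progress and create maintenance plans". It does not say what its weeks count from.
- **Table 1 (section 1.3.8).** The origin is screening: "Phone screening (w0". Baseline is w1, and the activity monitor has "Baseline evaluation (w1- 2), follow-up (w15". The habit measure is at "Treatment session 1,3,5,7,9 (w 3, 5, 7, 9, 11".
- **Section 2.3.** Baseline is week 0, and primary and secondary outcomes are measured again one week after the intervention. The habit measure is given fortnightly over sessions 3 to 11.

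Section 2.1 reports feasibility descriptively and expresses outcomes as Cohen's d. Section 2.2 states that no power analysis was used.

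**The concern.** A reader who tries to put every label on one calendar fails. Week 0 is phone screening in Table 1 and baseline in section 2.3. The first session is in week 2 in section 1.3.7 and at w3 in Table 1. The habit measure starts at session 1 in one place and at session 3 in another.

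Three things could be at stake. First, Hypothesis 2 concerns outcomes at the end of the intervention, and behaviour measured one week after the last contact is not the same quantity as behaviour measured three weeks after it. Second, section 2.1 plans a before-and-after effect size for habit formation, whose end points would move if the sessions differ. Third, if section 1.3.7 counts study weeks, a week-2 first session could fall while a treated participant is still wearing the baseline monitor (w1-2). That would contaminate baseline sedentary time in one arm only.

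**Working it through.** **1. The plan's own interval.** The session and week pairs in Table 1's habit row are 1→3, 3→5, 5→7, 7→9 and 9→11, so week = session + 2 every time. Table 1 stops at session 9. If weekly sessions continue, session 12 is at 12 + 2 = w14. Equally, 12 weeks starting at w3 end at 3 + 12 − 1 = w14. Follow-up is at w15, and 15 − 14 = **1 week**, as section 2.3 states.

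**2. Section 1.3.7 on its own.** Sessions: 1 (welcome) + 1 (pain) + 9 (weeks 3 to 11) + 1 (closing) = 12. Labelled weeks: 12 − 2 + 1 = 11. The count of 12 sessions holds only if week 3 has two. This mismatch is internal to the section and holds on any scale.

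**3. Section 1.3.7 placed on Table 1's scale.** Add a shift to its week labels:

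| Shift | First session | Closing session | Gap to w15 |
|---|---|---|---|
| 0 | w2 | w12 | 3 weeks |
| +1 | w3 | w13 | 2 weeks |
| +2 | w4 | w14 | 1 week |

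Only the +2 shift agrees with the interval in section 2.3. Only the +1 shift puts the first session at Table 1's w3. No shift does both, because section 1.3.7 spans 11 weeks and not 12.

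**4. Habit measure.** Suppose Table 1 numbers only the habit-formation sessions. Session k of these is in section 1.3.7's week k + 2. Two sessions (welcome and pain) precede them, so its overall number is also k + 2. For k = 1, 3, 5, 7, 9 this gives weeks 3, 5, 7, 9, 11 and overall sessions 3, 5, 7, 9, 11, which is the schedule in section 2.3. If instead Table 1 numbers all sessions and its weeks are study weeks, sessions 3 to 11 fall at w5, w7, w9, w11 and w13. Four of the five weeks are then shared, and the schedules differ only at one end each (w3 against w13).

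**5. Baseline monitor overlap.** Take a visit on day d of week 1 (d = 1 to 7), wear from d to d + 6, the second dietary recall on d + 2, and session 1 on day s. Overlap = max(0, d + 7 − s).

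- Section 1.3.7 as study weeks (s = 8 to 14), with session 1 no sooner than the day after the second recall (s ≥ d + 3): the maximum is d + 7 − (d + 3) = 4 of 7 days, or 5 if wear starts the day after the visit.
- Session 1 at w3 (s ≥ 15): the last wear day is at most 7 + 6 = 13, so the overlap is 0. If wear starts a day later, the last day is 14 and the overlap is still 0.

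A positive overlap therefore needs both the study-week reading and randomisation before wear ends. Section 1.3.5 puts the eligibility check after baseline evaluation. Criterion (h) in section 1.3.1 needs the dietary score, which section 1.3.4 takes from two recalls. The note to Table 1 says both primary outcomes feed the eligibility decision, and section 1.3.4 still calls the wearer a potential participant.

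**The case for a change.** The strongest reply is that the reconciliations in steps 1 and 4 do not sit comfortably together. If Table 1's habit row counts only habit-formation sessions and its weeks are study weeks, the ninth is at w11, the closing session is at w12, and the gap to w15 is 3 weeks again. To have both agreements, that row must use intervention weeks while the rest of its column uses study weeks. A reader should not have to infer this. The protection against overlap is also partly indirect: section 1.3.1 contains no sedentary-time criterion, so waiting for the monitor data rests on the Table 1 note alone.

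The labelling part of this stands: no single scale clears every entry. What does not follow is that the timing of the primary outcome is open. Section 2.3 gives it as an interval, which needs no week origin. The 3-week reading contradicts that statement and also shortens the programme to 11 weeks, against the 12 in sections 1.2 and 1.3.7. The habit schedules differ through session numbering, and the measure is given to the treatment group only, so no between-arm comparison depends on it. Early randomisation is a possibility that the text does not show. A sentence requiring staff to wait for the baseline data would restate what the eligibility rules and the Table 1 note already imply. Sections 1.3.5, 2.1 and 2.3 are partly in the past tense, so such a sentence might also come too late to act on.

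**Conclusion.** The labels are inconsistent and the sponsor would have to reconcile them in any later edition; this review does not say which calendar applies. It is a clerical slip with no consequence for design or analysis. The size is 12 sessions in 11 labelled weeks, two meanings of week 0, and two numberings of the habit sessions. Follow-up is stated as one week after the intervention and Table 1 reproduces it. Readings of 2 or 3 weeks come from mixing scales. Table 1 gives no arm-specific follow-up week, so none of these readings shows a bias between arms. Week labels enter no formula, test or sample-size figure, and harmonising them would alter no result.

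This rests on three assumptions. Weekly sessions continue from session 9 to session 12. Staff apply the eligibility rules as written before randomising. Figures 2 and 3, and the Table 2 of session content that section 1.3.7 cites, which are not in the text available here, do not contradict the interval in section 2.3. If treatment did start before baseline wear ended, the overlap would be at most 4 of 7 days (5 with next-day wear). Its effect on the estimate cannot be quantified from the documents.

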1.3.8 Follow-up data collection

When the 12-week intervention period is over, the coordinator will assign raters for follow-up evaluation. Most of the measures will be re-administered.

Table 1 Overview of measurements and testing time

Evaluation time point (week)	Variable	Measure
Screening		
Phone screening (w0)	Eligibility	1. Phone screening eligibility form
	Frailty status	2. Paulson Lichtenberg Frailty Index (PLFI)
	Cognitive impairment	3. The Six Item Cognitive Impairment Test (6CIT)
Primary outcome*		
Baseline (w1), follow-up (w15)	Sedentary time	4. Community Healthy Activities Model Program for Seniors (CHAMPS)
Baseline evaluation (w1- 2), follow-up (w15)	Sedentary time	5. ActivPal kcal expenditure
Baseline (w1, 2 nd phone follow-up), follow-up (w15, 2 nd phone follow-up)	Dietary quality	6. Automated Self-Administered 24-hour (ASA24) dietary recall
Secondary outcome		
Baseline (w1), follow-up (w15)	Frailty status	7. The Fried's Frailty Criteria 
 • Grip strength with dynamometer • 15 ft walking test
	Lower extremity muscle strength	8. Short Physical Performance Battery (SPPB) 
 • 3-meter walking test
	Balance	
	Quality of life	9. The World Health Organization Quality of Life- BREF (WHOQOL-BREF)
Habit formation (Treatment group only)	Habit formation	10. The self-reported habit index subscale
Demographics and other mediators		
Baseline (w1)	Comorbidities	11. Comorbidity Checklist
	Sociodemographic	12. Sociodemographic Form
Baseline (w1), follow-up (w15)	Participants anthropologies	13. Participants anthropologies forms 
 • Weight • Height • Waist circumference
	Depressive symptoms	14. Geriatric Depression Short form (GDS)
Treatment session 1,3,5,7,9 (w 3, 5, 7, 9, 11)	Habit formation	15. Self-report habit index (SRHI)

Note. *Both primary outcomes will be used for screening potential participants' eligibility.

2. Data analysis plan

2.1 Data analysis

Feasibility outcomes such as recruitment, retention, and attendance data were presented by descriptive statistics. Differences in baseline characteristics between the two groups were tested by independent t tests or chi-square/Fisher's exact tests. For the primary and secondary outcomes, effect sizes were represented by Cohen's D, where 0.2 indicates small, 0.5 as moderate, and 0.8 as large effects. As for mechanisms of behavior change, pre and post habit formation effect sizes are estimated by Cohen's D. All statistical analyses were conducted by IBM SPSS software, version 26.0 (SPSS Inc., Chicago, IL).

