1.1 Objectives and Hypotheses

The main objective of the SHAPE pilot study is to determine the feasibility of using Habit Formation (HF) treatment to increase Physical Activity (PA) (reduction in daily in hours of sedentary time), and dietary among prefrail African Americans. This study will test two hypotheses:

***Hypothesis 1:** The SHAPE study will demonstrate good feasibility with high recruitment rate and successfully administrating all of measures among the target population.*

***Hypothesis 2:** Treatment group participants will demonstrate greater increases in primary outcomes (sedentary time and dietary quality) and secondary outcomes (prefrailty reduction, lower extremity strength, balance, and quality of life) at intervention completion.*

[figure not shown]

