1.3 Study design

The SHAPE pilot study is a two-armed, single blinded, randomized control trial study (Figure 2). Community dwelling prefrail African Americans ages 55 and older is the target population to account for accelerated aging among African Americans.⁶⁶ The sampling frame are African American adults who register in the Healthier Black Elders Center's Participant Resource Pool (PRP). The screening, consent, and enrollment procedures will follow a strict IRB-approved protocol over 16 weeks. Eighty prefrail African Americans will be randomized to the treatment or control group.

[figure not shown]

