2.2 Sample size estimation

We did not use power analysis to estimate study sample size for determine efficacy. We aim to recruit 15 participants in per group suggested for feasibility pilot study.

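### Feasibility is the main objective and the only basis for 15 per group, yet its rates are planned without any measure of uncertainty, and at that size a retention rate may not be distinguishable from a materially lower one

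*Combined protocol and SAP*

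**What the plan says.** Section 1.1 puts feasibility first: "The main objective of the SHAPE pilot study is to determine the feasibility of using Habit Formation (HF) treatment". Hypothesis 1 in that section expects "good feasibility with high recruitment rate and successfully administrating all of measures among the target population". It gives no numerical target, and it mentions neither retention nor attendance.

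Section 2.1 states the whole analysis: "Feasibility outcomes such as recruitment, retention, and attendance data were presented by descriptive statistics". The list is open-ended, but completion of the measures, the second half of Hypothesis 1, is not named in it.

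Section 2.2 sets power aside ("We did not use power analysis to estimate study sample size for determine efficacy") and continues: "We aim to recruit 15 participants in per group suggested for feasibility pilot study". It does not say what precision that number gives. Section 1.3 states a different size: "Eighty prefrail African Americans will be randomized to the treatment or control group". Section 1.3.5 sets the allocation: "Participants will be allocated using a 1:1 ratio".

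Section 1.3.7 describes the treatment as "delivered to each participant during 12 face-to-face, home based sessions". The control group receives newsletters and telephone calls, so session attendance can be measured in the treatment arm only. Section 1.3.6 has recruitment done by cold calls to people on a registry list. The number to be called is not given.

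**The concern.** A sample chosen for feasibility is justified by how well it estimates feasibility rates. The plan neither states that precision nor asks for it to be reported. With 15 or 30 people, a percentage on its own hides a range wide enough to change the reading of the result, and whoever plans a later trial would carry that percentage forward as if it were known.

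Attendance has a further weakness. With up to 12 sessions per treated person, 15 people give 15 × 12 = 180 possible sessions. A percentage of 180 looks precise, but missed sessions tend to cluster in the same people: one participant who stops early loses many at once. The plan does not say whether attendance is summarised per person or per session, so that choice could be made after the data are seen.

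**Working it through.** **Inputs from the documents.** 15 per group, 30 in all (section 2.2); 80 in all, 40 per arm at 1:1 (sections 1.3 and 1.3.5); 12 sessions per treated participant (section 1.3.7). No significance level, power, effect size or precision target lies behind the 15, so there is no figure to reproduce. **Assumptions.** The observed counts, the number approached, the true rates, the standard deviation of sessions attended and the intraclass correlation (ICC) are illustrations. The documents give none of them.

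**1. Retention.** The exact (Clopper-Pearson) 95% limits for x out of n are the 2.5% quantile of Beta(x, n−x+1) and the 97.5% quantile of Beta(x+1, n−x). For 24/30 these are Beta(24, 7) and Beta(25, 6).

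| Observed | Rate | Exact 95% CI |
|---|---|---|
| 24/30 | 80% | 61.4 to 92.3% |
| 27/30 | 90% | 73.5 to 97.9% |
| 12/15 (one arm) | 80% | 51.9 to 95.7% |
| 13/15 (one arm) | 87% | 59.5 to 98.3% |
| 15/15 (one arm) | 100% | 78.2 to 100% |
| 64/80 | 80% | 69.6 to 88.1% |
| 72/80 | 90% | 81.2 to 95.6% |

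The interval for 24/30 is 92.3 − 61.4 = 30.9 points wide. For 13/15 it is 98.3 − 59.5 = 38.8 points.

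**2. How often a lower true rate looks acceptable.** This is the binomial tail P(X ≥ r | n, p). If true retention is 70%, the chance of observing at least 80% is 16.0% with n = 30 (r = 24), 29.7% with n = 15 (r = 12) and 3.0% with n = 80 (r = 64). The chance of at least 27/30 is 0.9% if the true rate is 70%, but 12.3% if it is 80%.

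**3. Recruitment.** The denominator is the people called or screened. With 30 enrolled:

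- 30/100 = 30%, CI 21.2 to 40.0%
- 30/200 = 15%, CI 10.4 to 20.7%
- 30/300 = 10%, CI 6.8 to 14.0%

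**4. Attendance.** If sessions were pooled, the approximate half-width is 1.96 × √[p(1−p) × DE / 180], with design effect DE = 1 + (12 − 1) × ICC. At p = 0.85:

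- ICC 0: DE = 1.0, half-width 5.2 points
- ICC 0.1: DE = 2.1, half-width 7.6 points
- ICC 0.3: DE = 4.3, half-width 10.8 points
- ICC 0.5: DE = 6.5, half-width 13.3 points

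An interval that ignored clustering would thus be about half its proper width at ICC 0.3 (5.2/10.8 = 0.48). With the participant as the unit, the half-width for mean sessions attended is t(0.975, 14 df) × SD/√15. That is 1.11, 1.66 or 2.22 sessions for an SD of 2, 3 or 4.

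**The case against.** Descriptive reporting of feasibility counts is ordinary in a pilot, and section 2.2 openly disclaims power for efficacy. The wording of section 2.1 does not rule out intervals. If counts and denominators are published, any reader can compute exact limits for recruitment and retention. All of that stands, and it keeps the point modest. It does not remove it, because section 2.1 commits to no denominators, and a participant-level interval for attendance cannot be recovered from a published percentage.

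Several stronger readings are tempting, and the documents do not support them:

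- *A high rate cannot be told from a poor one.* Too strong. An observed 27/30 excludes true rates below 73.5% and would arise only 0.9% of the time at a true 70%. Thirty people separate large gaps but not moderate ones. What counts as poor also needs a threshold, and the plan sets none.
- *All feasibility rates rest on about 30 people.* Not so for recruitment, the only rate Hypothesis 1 names. It rests on the people called.
- *Retention and attendance are what Hypothesis 1 tests.* It names recruitment and administration of the measures. Retention and attendance enter as feasibility outcomes through section 2.1.
- *Attendance will be pooled over sessions, or retention compared between arms.* The plan says neither. Both are possibilities left open.
- *The sample is 30.* Section 1.3 says eighty. At that size the intervals are clearly narrower.

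**Conclusion.** The point holds in a limited form. The trial's main question is to be answered by rates reported without uncertainty, from a sample justified only for that question. If 15 per group is the true size, 80% retention overall is compatible with anything from 61.4 to 92.3%, and a single-arm figure of 13/15 with 59.5 to 98.3%, so a materially lower rate may not be excluded. If eighty are randomised, 90% retention carries 81.2 to 95.6%: the problem shrinks, but reporting the interval is still worthwhile. The precision of recruitment cannot be judged until the number called is known.

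The retention intervals treat participants as independent and the observed counts as illustrations. The pooled-attendance figures also depend on an ICC for which the documents give no basis. The point concerns the uncertainty of the estimates. It does not show that the trial is too small to assess feasibility, nor does it say where a success criterion should lie. The change is worth making because it improves the answer to the main objective at almost no cost.

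**What to change.** In section 2.1, replace the descriptive-statistics sentence with a statement that:

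- recruitment (denominator: people called or screened, whichever is chosen, named in advance), retention (overall and by arm) and completion of the measures are reported as counts and proportions with exact Clopper-Pearson 95% confidence intervals;
- attendance is summarised per treated participant as sessions attended out of 12, with a 95% interval that takes the participant as the unit (a t interval or resampling of participants), not pooled sessions;
- any between-arm difference in retention that is reported carries a Newcombe 95% interval. As an illustration, 14/15 against 11/15 is a difference of 20 points with an interval of −8 to +46.

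In section 2.2, first reconcile 15 per group with the eighty in section 1.3. Then state the precision of the agreed size: for 90% retention, 73.5 to 97.9% with 30 randomised or 81.2 to 95.6% with 80.

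The cost is a few sentences and minutes of computation. Retention, attendance and completion need no new data; recruitment needs a count of the people called or screened. The downside is that the feasibility figures will look less certain.
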